The analyses for Haemo-QoL-A domain scores (Physical functioning, Consequence of bleeding, Role functioning) will be the same as the Total score analyses.

Additional analyses of efficacy endpoints

Correlation between FVIII activity and bleeding risk

The following analyses will be performed to investigate the correlation between FVIII activity levels and ABR:

- Using a cut-off of FVIII activity level (e.g., 5 IU/dL), each subject's data will be divided into 3 periods: baseline, from Week 5 to the first time reaching 5 IU/dL, and from the first time reaching 5 IU/dL to the end of the efficacy evaluation period. For each period, the duration of the period, the number of treated bleeds, the ABR, and the change in ABR from baseline will be listed and summarized.
- Based on the FVIII activity visit windows (Appendix 20.1 Visit Windows), median FVIII activity and total number of treated bleeds (defined in Section 13.2) will be calculated for each window for every subject. The total number of treated bleeds in each window will be plotted against the corresponding FVIII activity level to show the FVIII activity level around the time of bleeding. In addition, a negative binomial regression will be performed, using the number of treated bleeds in each window and the FVIII activity level in the window to model the relationship between the FVIII activity level and ABR. The SAS GENMOD procedure will be used where a REPEATED statement is included to account for within-subject correlation.
- ABR will be summarized in subgroups of subjects determined by the FVIII activity levels measured at Weeks 23-26, Weeks 49-52, Week 104, as well as by the peak FVIII activity levels.

Joint analysis of ABR and exogenous FVIII/emicizumab use

Per the study protocol, subjects will discontinue their regular prophylactic FVIII treatment regimen starting Week 5 post the day of BMN 270 infusion and switch to an episodic treatment schedule. In addition, subjects who experience recurrent bleeding episodes may resume their prior FVIII prophylaxis or start prophylactic emicizumab treatment. Because ABR and exogenous FVIII/emicizumab use are not independent, the following analyses will be performed to jointly assess ABR and exogenous FVIII/emicizumab use:

- Paired analysis of ABR and exogenous FVIII/emicizumab use in each of the efficacy evaluation periods defined in Section 13.1. This analysis enables the interpretation of ABR in the context of exogenous FVIII/emicizumab use.

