5.1 Analysis Populations

Intention-to-treat (ITT) population: all subjects who received BMN 270 infusion in 270-301.

Modified intention-to-treat (mITT) population: subjects who received BMN 270 infusion in 270-301 and were HIV-negative at study screening.

Study 270-902 rollover subjects: subjects who completed approximately 6 months' participation in the BioMarin-sponsored non-interventional study 270-902 before enrolling in 270-301, were HIV-negative at study screening, and received BMN 270 infusion in 270-301.

Directly enrolled subjects: subjects who were enrolled in 270-301 without prior 270-902 participation and received BMN 270 infusion in 270-301.

Directly enrolled, HIV-negative subjects: subjects who were directly enrolled in 270-301 and HIV-negative at study screening.

Study 270-902 rollover subjects will be used for the primary analysis of the primary efficacy endpoint and the second-ranked secondary efficacy endpoint of annualized utilization (IU/kg/year) of exogenous FVIII replacement therapy, the mITT population will be used for the primary analysis of the first-ranked secondary efficacy endpoint of FVIII activity based on the chromogenic substrate assay and tertiary efficacy endpoints, and the ITT population will be used for the primary safety analysis.

Unless otherwise specified, all data will be summarized and presented side-by-side for all 5 analysis populations for comparison purposes. If not used for the primary analysis, an analysis population may be used in supportive analyses of the efficacy and safety, as specified in Sections 13 and 14.

When applicable, additional sensitivity analyses may be carried out for the Per-Protocol (PP) analysis population, defined as a subset of the ITT population who are compliant with the

Study 270-301 Statistical Analysis Plan

protocol and do not have major protocol violations that affect the interpretability of efficacy data. The PP population will be determined by team data review; reasons for excluding subjects will be defined prior to database lock and documented in the clinical study report (CSR).

In addition, exploratory analyses of efficacy and safety may be performed on a subset of subjects with longer follow-up time (eg, 3 years) at the time of the 2-year analysis.

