13.2.4 Sensitivity Analysis Methods for Primary Efficacy Endpoint

The primary analysis will be conducted for the PP population when applicable.

If a subject restarts FVIII prophylaxis, starts emicizumab, or discontinues from the study prior to the cut-off for the analysis, a sensitivity analysis will be performed where the post-baseline ABR for treated bleeds is imputed as the same as the baseline ABR for treated bleeds (ie, the change in ABR is 0).

The primary analysis will also be performed with baseline (prior to BMN 270 infusion while receiving FVIII prophylaxis) values calculated using the data starting from 12 months prior to study enrollment. P-values will be provided for descriptive purpose only.

The ABR for treated bleeds will be analyzed using a generalized linear mixed model assuming negative binomial as the underlying distribution. The model will include period (pre-BMN 270 infusion [baseline period], Weeks 1-end of FVIII Prophylaxis, Post FVIII Prophylaxis-Last Visit) as the only factor. The analysis will be performed using the SAS GENMOD procedure where the duration of each period is included as an OFFSET to account for varying follow-up times and a REPEATED statement is included to account for the intra-patient comparison. In addition, the change from baseline (prior to BMN 270 infusion while receiving FVIII prophylaxis) in the ABR for treated bleeds in the efficacy evaluation period ("Post FVIII Prophylaxis to Last Visit") will also be tested using Wilcoxon signed-rank test.

The details of the sensitivity analyses are listed in [Table 13.2.4.1](#).

	Study 270-301 Statistical Analysis Plan
---	--

Table 13.2.4.1: Primary and Sensitivity Analyses of Primary Efficacy Endpoints

Endpoint	Analysis	Analysis population	Analysis period	Imputation	Analysis method

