13.3.4 Correlation between FVIII Activity and Bleeding Risk

FVIII activity is widely acknowledged to be a key aspect of hemophilia A and a valuable indicator of patients' status, while annualized bleeding rate has been traditionally used as the primary clinical endpoint for replacement therapy. The correlation between FVIII activity level and bleeding risk has been researched, showing that increases in FVIII activity levels are predictably associated with a decreased number of annual bleeds ([den Uijl, 2011](#)). The following analyses will be performed to explore the relationship between measured FVIII activity and bleeding in this study.

- Using a cut-off of FVIII activity level, e.g., 40 IU/dL, each subject's data will be divided into 3 periods: baseline, from Week 5 to the first time reaching 40 IU/dL, and from the first time reaching 40 IU/dL to the end of efficacy period. For each period, the duration of the period, the number of bleeds, the ABR, and the change in ABR from baseline will be listed and summarized. ABR will also be estimated using negative binomial regression modelling number of treated bleeds vs period with period duration as the offset, repeated within subject. The analysis will be performed using various cut-off, such as 5, 15, 25, 30, 40 IU/dL.
- Based on the FVIII activity visit windows ([Appendix 20.1 Visit Windows](#)), median FVIII activity and total number of treated bleeds (defined in [Section 13.2](#)) will be calculated for each window for every subject. The total number of treated bleeds in each window will be plotted against the corresponding FVIII activity level to show the FVIII activity level around the time of bleeding. A negative binomial regression will be performed, modelling number of bleeds in each window vs. FVIII activity in the window, repeated within subject (the "repeated" term may be removed in case of convergence difficulty due to small sample size). The analysis will be done for FVIII activity measured by one-stage clotting assay and chromogenic assay separately. The same analyses will be conducted for treated joint bleeds.
- ABR will be summarized in subgroups of subjects determined by the FVIII activity levels as measured at Weeks 23-26, Weeks 49-52, Week 104, as well as by the peak FVIII activity levels.

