For comparison purposes, similar analyses will be performed to assess the natural decline of FVIII activity while subjects are on or off immunosuppressants. Changes in FVIII activity levels between 4 weeks before and 4 weeks after Week 20, 24, 28, et al. will be plotted separately for subjects who ever or never received immunosuppressant therapy.

The above analyses will be repeated for select concomitant medications (e.g., lamivudine) to assess the impact of such on FVIII expression in the mITT subjects who have discontinued them before the data cut-off date for the 2-year analysis.

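### The window-level bleed-versus-FVIII regression names no offset although its windows run from 28 to 49 days; the slope is pushed more negative, mainly by follow-up beyond Week 104

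*SAP*

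**What the plan says.** The second bullet of SAP Section 13.3.4 takes median FVIII activity and the number of treated bleeds in each Appendix 20.1 window for each subject. It then fits a negative binomial regression, "modelling number of bleeds in each window vs. FVIII activity in the window, repeated within subject". The model is run separately for the one-stage and chromogenic assays and again for treated joint bleeds. The repeated-measures term may be dropped if the model does not converge. The synopsis describes the same model and says that it serves "to model the relationship between the FVIII activity level and ABR". Neither place names an offset or any other exposure term.

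The SAP does name one for its period-based negative binomial models. The first bullet of Section 13.3.4 describes "modelling number of treated bleeds vs period with period duration as the offset, repeated within subject". In the sensitivity model for the primary endpoint (Section 13.2.4), "the duration of each period is included as an OFFSET to account for varying follow-up times".

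Appendix 20.1 lists the FVIII windows. Weeks 23-26 (Days 159-186) stands in the list between Weeks 21-24 (Days 145-172) and Weeks 25-28 (Days 173-200). Section 13.3.4 excludes none of them from the regression.

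**The concern.** Section 13.2 defines ABR per day of observation. A count over windows of unequal length is not a rate unless the model carries the exposure. At the same bleeding rate, a 49-day window is expected to hold 1.75 times the bleeds of a 28-day window.

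The long windows are not spread evenly over time: most come after Week 104. The SAP expects activity to fall, since Section 13.3.7 plans to "assess the natural decline of FVIII activity while subjects are on or off immunosuppressants". Extra days at risk then coincide with lower activity, and the model reads them as extra bleeding at low activity. That moves the slope in the direction that Section 13.3.4 expects to find. The same omission runs through both assays and the joint-bleed version.

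The overlap is a second, smaller matter: each bleed on Days 159-186 falls in two windows.

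**Working it through.** The SAP gives no slope, power or sample size for this model, so there is no figure to reproduce.

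**Step 1. Window lengths** (Appendix 20.1; length = last day - first day + 1).

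| Window | Days | Length | Ratio to 28 |
|---|---|---|---|
| Weeks 5-8 to 49-52, each | 33 to 368 | 28 | 1.00 |
| Week 56 | 369-406 | 38 | 1.36 |
| Weeks 60 to 100, each | 407 to 714 | 28 | 1.00 |
| Week 104 | 715-743 | 29 | 1.04 |
| Week 110 | 744-792 | 49 | 1.75 |
| Week 116 | 793-835 | 43 | 1.54 |
| Weeks 122 to 146, each | 836 to 1045 | 42 | 1.50 |
| Week 152 | 1046-1079 | 34 | 1.21 |
| Week 156 | 1080-1117 | 38 | 1.36 |

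**Step 2. Overlap.** Days 159-172 (14 days) lie in both Weeks 21-24 and Weeks 23-26. Days 173-186 (14 days) lie in both Weeks 23-26 and Weeks 25-28. So 28 days are covered twice: 28/711 = 3.9% of Days 33-743. No other FVIII windows through Week 162 overlap. Without Weeks 23-26, each day from Day 2 is covered once.

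**Step 3. Who contributes long windows.** The evaluation period runs to the last visit by data cut-off (Section 13.1). Section 5.1 foresees a "subset of subjects with longer follow-up time (eg, 3 years) at the time of the 2-year analysis" but gives no number, so the share reaching Week 156 is an assumption here: 0%, 15% or 100%.

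**Step 4. Artefact under no true association.** Assume that log activity falls 0.4 per year, that its between-subject SD is s, and that the bleeding rate is constant. The expected count is then proportional to window length L. With t the window midpoint in years, the no-offset slope is approximately

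b = -0.4 x [Cov(L,t) / mean(L)] / [s² + 0.4² x Var(t)].

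Windows are taken as listed from Week 5, with Weeks 23-26 included:

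| Share reaching Week 156 | mean(L) | Cov(L,t) | Var(t) | b, s = 1.0 | b, s = 0.8 | b, s = 0.3 |
|---|---|---|---|---|---|---|
| 0% (all end at Week 104) | 28.42 | 0.046 | 0.320 | -0.0006 | -0.0009 | -0.0045 |
| 15% | 29.07 | 0.942 | 0.418 | -0.012 | -0.018 | -0.083 |
| 100% | 31.80 | 3.643 | 0.707 | -0.041 | -0.061 | -0.226 |

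Example (100%, s = 0.8): 0.4 x 3.643/31.80 = 0.0458; 0.64 + 0.16 x 0.707 = 0.753; 0.0458/0.753 = 0.061. Solving the log-link estimating equation exactly gives -0.082 and -0.225 in the two cells where the approximation is loosest, and the same values elsewhere. A negative binomial dispersion of 1 makes no material difference.

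For scale, a slope of -0.018 makes a halving of activity look like a rate ratio of exp(0.018 x 0.693) = 1.01. A slope of -0.061 gives 1.04, and -0.225 gives 1.17. The true ratio is 1 throughout.

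**Step 5. With a true association.** A simulation assumed 134 subjects, 2 bleeds per year at zero activity, true slopes of -0.02 and -0.05 per IU/dL, and activity half-lives of 1 and 2 years after Day 180. Without the offset the slope was about 1-3% too steep if 15% of subjects reached 3 years, and about 4-14% too steep if all did. There were 25 runs per setting, so these are rough.

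**Step 6. The duplicate window alone.** In the same simulation, adding Weeks 23-26 moved the slope by less than 0.0004 and the robust standard error by about 1%. In Step 4, dropping it changes the slope at s = 0.8 from -0.0608 to -0.0607 (100%) and from -0.0183 to -0.0185 (15%).

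**The case against.** The best defence is that the SAP is silent on the offset and does not exclude one. The aim is stated in terms of ABR, the neighbouring models use duration, and Section 5.4 allows annualized values from windows where deemed appropriate. A programmer might well add the offset unprompted. That may be so, but Section 5.4 is permissive and does not define this model. Naming the offset in one bullet and not in the next gives the programmer no instruction to use it. A reader might infer that the reported slope was in fact produced without an offset; the SAP cannot show that.

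It is also fair that the size depends on follow-up. From Week 5 to Week 104 the windows are nearly equal and the artefact is close to nil. A reader might take about -0.06 per log-unit as its size, but that needs every subject to reach Week 156 and an assumed SD near 0.8. The SAP speaks only of a subset with longer follow-up and gives neither figure.

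A reader might also infer that double counting inflates the bleeding rate. It does not. The duplicate window repeats bleeds, exposure and activity together, so it only gives one month more weight. Weeks 23-26 serves elsewhere as a milestone window (Section 13.3.2), which probably explains its place in the list. The repeated-measures term covers the duplication while it is kept, although the SAP lets it be dropped.

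Finally, Section 13.3.4 is exploratory and lies outside the nine-step hierarchy of Section 13.7. The same question is also addressed by a period model with an offset and by ABR summaries in activity subgroups. This stands, and it limits the severity.

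**Conclusion.** Wrong as written, of minor severity. Followed literally, Section 13.3.4 relates counts over unequal exposure to activity while claiming to describe a rate. Where activity declines over time, the slope is too negative.

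With no true association, a decline of 0.4 log-units per year and a between-subject SD of log activity from 1.0 to 0.3, the artefact per log-unit is:

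- about -0.001 to -0.005 if follow-up ends at Week 104;
- about -0.01 to -0.08 if 15% of subjects reach Week 156;
- about -0.04 to -0.22 if all do.

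The decline, the SD and the follow-up shares are assumptions, since the SAP gives none of them. The direction depends on activity falling. The duplicated Days 159-186 are a real untidiness with negligible effect on the slope. No primary or ranked secondary conclusion is touched.

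**What to change.** In the second bullet of Section 13.3.4 and the matching synopsis bullet, state two things:

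- The offset is the log of the number of days of the window on which the subject was observed within the evaluation period. This also handles windows cut short by a late start of the evaluation period, withdrawal or last visit.
- The Weeks 23-26 milestone window is not used in this regression, so that each day is counted once.

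Apply both to the one-stage, chromogenic and joint-bleed versions. The cost is one sentence in two places and a rerun of these models if they were fitted without the offset. No new data are needed, and the change matches what the SAP already does in its other period-based negative binomial models.

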**Study 270-301 Statistical Analysis Plan**

negative subjects (22 actual, including 2 HIV-positive subjects who were enrolled prior to Protocol Amendment 3 [dated 24 August 2018] that suspended further enrollment of HIV-positive subjects) were planned to enroll in the study with at least 12 months of retrospectively collected well-documented, high-quality historical data concerning previous bleeding episodes and exogenous FVIII usage, while approximately 110 HIV-negative subjects (112 actual) were planned to enroll in the study after having completed at least 6 months' participation in the BioMarin-sponsored non-interventional Study 270-902, in which bleeding and FVIII use data prior to gene therapy while on FVIII prophylaxis were prospectively collected.

In order to minimize bias in the ongoing study and to assure safe and ethical conduct of the clinical trial, an independent Data Monitoring Committee (DMC), consisting of experts in clinical trials, statistics, and hemophilia, has been convened. The DMC has sole access during the trial to amalgamated FVIII activity levels, FVIII usage, and bleeding data, reviews available safety and efficacy (e.g., FVIII activity) data during the study on an ongoing basis, and may determine, based on emerging data and the risk/benefit profile, that further enrollment at 6E13 vg/kg should be discontinued in favor of a different dose of BMN 270, not to exceed 6E13 vg/kg. If the DMC recommends a dosing modification, then additional subjects may be enrolled, up to a total of approximately 130 subjects, at the new BMN 270 dose level (regardless of the number of subjects previously enrolled at 6E13 vg/kg).

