4.5 Sample Size Determination

Approximately 130 subjects (134 actual) were planned to be dosed in the study. The sample size for this study was based on clinical and statistical considerations in order to provide sufficient data to assess both safety and efficacy of BMN 270.

For the primary endpoint of change from baseline in ABR for treated bleeds, the primary analysis will be performed utilizing bleeding episode data from the study 270-902 rollover subjects. For the analytic sample size calculation of ABR, it is assumed that the pre- and post-BMN 270 infusion population mean ABRs are 3.5 and 1 respectively, and the distribution of ABRs is negative binomial distribution with a dispersion parameter of 2.2. Given the underlying negative binomial distributions, the standard deviations of the pre- and post-BMN 270 infusion ABRs are calculated as 7.8 and 1.8, respectively. The mean (SD) of the change from the pre- to post-BMN 270 infusion ABRs are calculated as -2.5 (8), assuming the correlation between pre- and post-BMN 270 infusion ABRs is zero. Under this assumption, an analytic sample size of 110 will have at least 95% power to demonstrate that the change from baseline (prior to BMN 270 infusion while receiving FVIII prophylaxis) in ABR during Post FVIII Prophylaxis to last visit is less than 3.5 (non-inferiority margin), using a one-sample t-test with a 2-sided significance level of 0.05. Under the same

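### The exploratory bleed-versus-FVIII window model may lose its only within-subject term on non-convergence, which would understate the standard error if bleeding and FVIII activity both cluster by subject

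*SAP*

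**What the plan says.** Section 13.3.4 of the SAP explores how FVIII activity relates to bleeding. In its second bullet, median activity and the number of treated bleeds "will be calculated for each window for every subject", so each subject supplies many rows. The regression is described as "modelling number of bleeds in each window vs. FVIII activity in the window, repeated within subject". A parenthesis adds that the repeated term "may be removed in case of convergence difficulty due to small sample size". The section does not say what counts as convergence difficulty, offers no other way to account for clustering, and does not require the report to state which model was fitted. The analysis is run for each of the two assays and again for treated joint bleeds.

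The synopsis (section 1, on the correlation between FVIII activity and bleeding risk) describes the same model without an exit: "The SAS GENMOD procedure will be used where a REPEATED statement is included to account for within-subject correlation". The other repeated negative binomial models, in section 13.2.4 and in the first bullet of section 13.3.4, have no such exit either.

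**The concern.** The repeated term is the model's only allowance for several rows coming from one subject. The negative binomial dispersion parameter does not replace it: it adds variance to each row but does not link the rows of a subject. Without the term, a subject who bleeds often at a persistently low activity level counts as many separate pieces of evidence for the relationship. The slope is not biased by this in itself, but its stated precision is too high. At stake is how firmly the study report can describe the activity-bleeding relationship. The two descriptions of one model also disagree, so a programmer working from the synopsis and one working from section 13.3.4 could fit different models.

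**Working it through.** The plan gives no figure for this model, so there is none to reproduce. The check asks how far the standard error falls short under the plan's own planning values.

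**Inputs from the SAP**
- Windows: Appendix 20.1 lists 12 non-overlapping FVIII windows from Week 5-8 to Week 49-52 and 13 from Week 56 to Week 104, so 12 + 13 = 25. Week 23-26 (Days 159 to 186) overlaps its neighbours and is not counted.
- Subjects: "Approximately 130 subjects (134 actual) were planned to be dosed in the study". Removing the 2 HIV-positive subjects gives 134 − 2 = 132. Section 13.3.4 names no population, so the 112 rollover subjects were also tried.
- Bleeding rate: section 4.5 assumes that the pre- and post-infusion "population mean ABRs are 3.5 and 1 respectively", so 1 per year after infusion.
- Dispersion: k = 2.2 (section 4.5). Variance = mean + k × mean² gives a post-infusion SD of √(1 + 2.2) = 1.79, matching the plan's 1.8. The same formula gives 5.52 for the pre-infusion SD, where the plan has 7.8; that value is not used here.

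**Assumptions**
- The dispersion reflects a lasting subject effect. Milder values of 0.5 and 1, and 0, were also tried.
- A share s of FVIII variance lies between subjects. The SAP gives no value; the range tried was 0 to 0.95.
- All windows are 28 days. Two are slightly longer.

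**Approximation**
- Mean bleeds per window: m = 28/365.25 = 0.0767.
- Within-subject correlation of counts: r = k·m/(1 + k·m) = 0.1687/1.1687 = 0.144 at k = 2.2.
- Factor by which the standard error is too small: √(1 + 24·r·s).
 - s = 0.5: √(1 + 1.73) = 1.65
 - s = 0.8: √(1 + 2.77) = 1.94
 - s = 0.95: √(1 + 3.29) = 2.07

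**Simulation** (250 to 300 runs per case). This compares negative binomial regression with no repeated term against the same mean model with subject as cluster, independence working correlation and robust standard errors. The true slope is 0 and n = 132 unless stated. The ratio is the mean unclustered standard error divided by the actual SD of the slope; the factor is its inverse.

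| k | s | Ratio | Factor | Rejection at nominal 5%, unclustered | Same, cluster-robust |
|---|---|---|---|---|---|
| 2.2 | 0.5 | 0.58 | 1.7 | 24% | 8% |
| 2.2 | 0.8 | 0.49 | 2.0 | 33% | 7% |
| 2.2 | 0.95 | 0.47 | 2.1 | 34% | 8% |
| 2.2 (n = 112) | 0.8 | 0.49 | 2.0 | 36% | 10% |
| 1 | 0.8 | 0.67 | 1.5 | 17% | 6% |
| 0.5 | 0.5 | 0.89 | 1.1 | 8% | 4% |
| 0.5 | 0.8 | 0.74 | 1.4 | 14% | 7% |
| 0.5 | 0.95 | 0.73 | 1.4 | 19% | 8% |
| 2.2 | 0 | 1.02 | 1.0 | 4% | 5% |
| 0 | 0 to 0.95 | 0.97 to 1.00 | 1.0 | 4% to 6% | 6% to 7% |

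At k = 2.2, s = 0.8 and n = 132 the figures behind the ratio are an actual SD of 0.140 against an unclustered standard error of 0.069; the cluster-robust value is 0.123. With a true slope of −0.4 in that setting the ratio is 0.52. With 250 runs, a rejection rate near 33% carries a simulation error of about √(0.33 × 0.67/250) = 3 percentage points. Fits that failed were left out: none at k = 2.2, 37 to 47 of 300 at k = 0.

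**The case against.** Several points on the other side stand. The section is exploratory and lies outside the nine-step testing sequence of section 13.7. The fallback is doubly conditional: it is a permission, and it applies only on convergence difficulty, which nothing shows to be likely with over 100 subjects. The first bullet of section 13.3.4 studies the same relationship by period with a repeated model and no exit, so a clustered analysis would remain.

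Four stronger readings are tempting, and the document does not support them.
- A reader might infer that a planned confidence interval or p-value would be invalid. The SAP specifies neither for this regression; what is affected is the standard error and any inference later built on it.
- A reader might treat FVIII activity as nearly constant within a subject and apply the full clustering factor. The SAP gives no such figure and expects change: section 13.3.2 summarises time to maximum and changes between milestones, and section 13.3.7 refers to natural decline.
- A reader might expect the worst understatement for treated joint bleeds. Rarer events lower the row-level correlation: at k = 2.2 and s = 0.8, an assumed joint-bleed ABR of 0.4 per year gives a factor of about 1.5, against 1.9 at 1 per year.
- A reader might think robust standard errors remove the problem entirely. They rejected in up to 10% of runs at a nominal 5%.

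The SAP also names no working correlation. If independence was already intended, the first step of a robust fallback could be the model that failed, so a second step is needed. None of this makes the unclustered model a valid replacement.

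**Conclusion.** The point holds as a minor one. Section 13.3.4 permits removal of the only within-subject term from a model with up to 25 rows per subject through Week 104, and the synopsis does not. Under the plan's ABR of 1 per year and dispersion of 2.2, with 0.5 to 0.95 of FVIII variance between subjects, the standard error would be too small by a factor of about 1.7 to 2.1. With dispersion of 0.5 to 1 the factor is about 1.1 to 1.5. If either bleeding or FVIII activity is uncorrelated within subject, there is no shortfall.

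The size rests on two things the SAP does not establish: that the planning dispersion is a lasting subject effect, and the share of FVIII variance between subjects. The direction does not depend on their exact values as long as both correlations are positive. No primary or secondary conclusion is affected.

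**What to change.** Replace the parenthesis in section 13.3.4 with wording such as: *If the model does not converge, the plain regression will be fitted with an independence working correlation and empirical standard errors clustered by subject, with a small-sample correction; if that also fails, a bootstrap resampling subjects will be used. Clustering by subject will not be removed, and the model used will be reported.* State what counts as non-convergence, and put the same rule in the synopsis so that the two descriptions agree.

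With an independence working correlation, the coefficient equations are those of the unclustered regression at the same dispersion value, so difficulty in estimating a working correlation is no reason to give up clustering. The cost is a sentence in two places and a little more programming. Robust standard errors can still be slightly liberal when events are few, which is why the small-sample correction is included.
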